#### **Recruitment, Randomization and Allocation**

Incoming undergraduate students to the University of Sheffield ( $N \approx 5000$ ) will be sent an email one month before the start of semester 1 with information about the study and a link to the baseline questionnaire. On completion of the baseline questionnaire participants will

be randomly allocated to one of two arms using a random number generator (as part of the LifeGuide software). Participants in both arms of the trial will be sent emails with links to the follow-up questionnaires using SurveyGizmo one and six months after starting university. All participants will receive three automatic reminders to complete the questionnaires at each time point. Participants in the intervention arm will also be sent automatic email prompts to use the intervention website after initially accessing the intervention website and shortly before the start of their second semester at university. Participants will receive incentives to complete the questionnaires by being entered into £100 prize draws at each time point. Participants who complete all three questionnaires will receive a £10 gift voucher and will be entered into a further prize draw for an iPad mini.

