## Measures

Primary outcome measures: Self-reported health behaviour will be measured using a mixture of reliable and validated measures as well items from the Health Survey for England (HSE) [5]. (i) *Fruit and Vegetable Consumption.* Fruit and vegetable consumption (portions per day) will be assessed using a two-item dietary questionnaire [6] which has been validated against bio-chemical markers (e.g., potassium excretion, urinary potassium/creatinine ratio and plasma vitamin C). (ii) *Physical Activity.* The International Physical Activity Questionnaire (IPAQ) will be used to assess levels of physical activity. Respondents indicate how many times, and for how long, they have engaged in vigorous exercise, moderate exercise and walking in the past 7 days. These values are then converted into METs (metabolic equivalent of task) to provide a total score. The IPAQ has undergone extensive reliability and validity testing across 12 countries [7]. The IPAQ items will be supplemented by more detailed questions on walking from the HSE. (iii) *Alcohol.* Alcohol consumption will be assessed using a retrospective seven-day diary in which participants are asked to report the amount of alcohol consumed on each of the past 7 days [8]. The total number of units of alcohol consumed in the past week (and the number of binge sessions) will be calculated. (iv) *Smoking.* Items based on the HSE [5] will be used to assess participants’ current smoking status (and the typical number of cigarettes/amount of tobacco smoked).

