Secondary outcome measures: (i) *Social cognitive variables.* Brief measures of social cognitive variables for each behaviour will be constructed in line with current recommendations [9]. These will include measures of attitude (e.g., “Engaging in binge drinking at university would be... good/bad”), norms (e.g., “Most people who are important to be think I should/should not engage in binge drinking at university”), self-efficacy (e.g., “If I wanted, I could easily engage in binge drinking at university”), perceived control (e.g., “Whether or not I engage in binge drinking at university is under my control”), intention (e.g., “I intend to engage in binge drinking at university”) and planning (e.g., “To what extent do you have a detailed plan about how to avoid binge drinking at university?”). (ii) *Health status* will be assessed using the EQ-5D-3L [10]. The EQ-5D-3L is a short, standardised measure of health status that assesses levels of severity (no problems/some or moderate problems/extreme problems) in five dimensions: mobility, self-care, usual activities, pain/discomfort, anxiety/depression. The measure provides a descriptive profile and a single index of health status. (iii) *Recreational drug use.* An indirect method of assessing recreational drug use will be used that maintains respondent anonymity [11]. Respondents will be asked to indicate the number of yes answers (0 or 5, 1, 2, 3, 4) to 5 questions – 4 of which have 50% population prevalence (e.g., odd or even date of birth) and 1 of which is on their use of recreational drugs. (iv) The Alcohol Use Disorders Identification Test (AUDIT) [12] will also be used to assess hazardous and harmful patterns of alcohol use. (v) *BMI.* Participants will record their height and weight to calculate BMI. (vi) *Health services usage.* Participants will be asked to report their use of health services (e.g., GP visits, hospitalisations). (vii) *Engagement with the digital intervention.* Various measures of engagement with the intervention will be recorded including the number of pages visited, the number of activities completed, etc.

Hair analysis: For participants who participate in the additional study of biochemical markers of health behaviour, the hair samples will be liquefied and analysed for biochemical markers of various health behaviours related to alcohol consumption, cigarette smoking, diet

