### **Analyses**

Both the data and the health economic analyses will follow the same procedure as outlined in the study protocol paper for the original U@Uni trial [14] and reported in the accompanying papers [1, 5]. Thus, multivariate analysis will be conducted to assess the impact of the intervention on each of the four targeted health behaviours at six-month follow-up, controlling for age, gender, nationality and baseline scores.

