## **Acknowledgements**

The study is funded by the UK National Prevention Research Initiative (NPRI) Phase 4 (grant number: MR/J0004501/1). The NPRI includes the following Funding Partners (in alphabetical order): Alzheimer's Research Trust, Alzheimer's Society, Biotechnology and Biological Sciences Research Council, British Heart Foundation, Cancer Research UK, Chief Scientist Office, Scottish Government Health Directorate, Department of Health, Diabetes UK, Economic and Social Research Council, Health and Social Care Research and Development Division of the Public Health Agency (HSC & R&D Division), Medical Research Council, The Stroke Association, Wellcome Trust, Welsh Assembly Government and World Cancer Research Fund.

Table 1. *Summary of Primary and Secondary Outcome Measures*

Measure	Baseline	One-month follow-up	Six-month follow-up
Primary Outcome Measures:			
Fruit and Vegetable Intake	x	x	x
IPAQ (Physical Activity)	x	x	x
Alcohol Use (Units)	x	x	x
Smoking Status	x	x	x
Secondary Outcome Measures:			
Number of binge sessions	x	x	x
Number of cigarettes	x	x	x
Intention (all HBs)	x	x	x
EQ-5D-3L (Health status)	x	x	x
BMI	x	x	x
Drug use	x	x	x
TPB variables/planning		x	x
AUDIT			x
Health services usage			x
Hair samples	x		x

Figure 1. *Flowchart of the Randomised Controlled Trial*

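### The primary models leave out baseline intention, a valid pre-randomisation covariate already collected for all four behaviours; adding it would probably bring a modest gain at almost no cost

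*Protocol*

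**What the plan says.** The protocol's Analyses section plans a multivariate analysis of "the impact of the intervention on each of the four targeted health behaviours at six-month follow-up", "controlling for age, gender, nationality and baseline scores". It also says that the analyses "will follow the same procedure as outlined in the study protocol paper for the original U@Uni trial".

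Table 1 has a row beginning "Intention (all HBs", marked at baseline, one month and six months. The remaining theory-of-planned-behaviour variables and planning start only at one month, so intention is the one social cognitive measure available at baseline.

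The Recruitment, Randomization and Allocation section fixes the order of events: "On completion of the baseline questionnaire participants will" then "be randomly allocated to one of two arms using a random number generator". Intention is therefore recorded before allocation.

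The Measures section gives one example of an intention item, for binge drinking: "I intend to engage in binge drinking at university".

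**The concern.** Baseline behaviour is measured about a month before the first semester, and physical activity and alcohol are recalled over the past seven days. The outcome is behaviour six months into university, in a different setting. Pre-university behaviour may therefore leave a good deal of outcome variance unexplained. An intention item framed around life at university looks forward to the setting of the outcome and may predict part of what is left. The intervention itself rests on theory-based messages and implementation intentions, so the trial's own reasoning links intention to later behaviour.

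A prespecified prognostic covariate measured before randomisation does not bias the comparison, and at about 1200 participants one extra parameter per model costs almost nothing. What is at stake is a possible small gain in precision or power on the co-primary comparisons, from data the trial already holds.

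**Working it through.** **Inputs from the protocol (Sample Size Calculations).** About 5000 students invited; response 31.34%; at least one follow-up point from 76.60% of respondents; 600 per arm; d = 0.20; two-sided significance level .0127; 80% power; overall effect of internet-based interventions d = 0.16.

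**Assumptions, not in the protocol.** R0², the share of outcome variance explained by the planned covariates: .09 to .25, which corresponds to a baseline-outcome correlation of .3 to .5. q, the share of the remaining variance explained by intention (partial R-squared): 2%, 5% or 10%. The normal approximation is used, with d on the raw SD.

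**Step 1: the plan's own figures.**
- 5000 × .3134 × .7660 = 1200.3, which matches 1200.
- 1 − .95^(1/4) = .01274, which matches .0127 for four endpoints.
- Needed per arm for 80% power without adjustment: 2 × (2.492 + 0.842)² / 0.20² ≈ 556. The claim that 600 per arm is sufficient is correct.
- Unadjusted power at 600 per arm: Φ(0.20 × √(600/2) − 2.492) = Φ(3.464 − 2.492) = 83.4%.

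**Step 2: power of the planned model.** The planned analysis already adjusts for baseline, so 83.4% is not the right comparator. With adjustment, power = Φ(d × √(n / (2(1 − R0²))) − 2.492).
- R0² = .09: Φ(3.631 − 2.492) = 87.3%.
- R0² = .25: Φ(4.000 − 2.492) = 93.4%.

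**Step 3: add intention.** Replace (1 − R0²) by (1 − R0²)(1 − q).

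| q | R0² = .09 | R0² = .25 | Gain (points) | SE reduction, 1 − √(1 − q) |
|---|---|---|---|---|
| 0 | 87.3% | 93.4% | – | – |
| 2% | 88.0% | 93.9% | 0.5 to 0.8 | 1.0% |
| 5% | 89.1% | 94.7% | 1.2 to 1.9 | 2.5% |
| 10% | 90.9% | 95.8% | 2.4 to 3.7 | 5.1% |

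**Step 4: two less favourable settings.**
- Fewer students at six months. The 76.60% retention figure counts anyone with at least one follow-up, whereas the primary analysis is at six months. At an assumed 500 per arm, the planned model has 79.5% to 87.7% power (unadjusted: 74.9%). With q = 10% this becomes 84.2% to 91.3%.
- Smaller effect. At d = 0.16, 600 per arm and R0² = .25, power goes from 76.1% to 78.1% at q = 4% and to 80.6% at q = 9%.

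**Step 5: smoking status.** Steps 2 to 4 are normal-theory results for continuous outcomes. If smoking status is analysed by logistic regression, a prognostic covariate can raise power, but it does not shrink the standard error of the log odds ratio, and it changes which conditional odds ratio is estimated. The table should not be applied to smoking.

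**The case against.** The strongest reply is that the plan contains no mistake here. Adjusting for demographics and baseline behaviour is conventional and sound, every stated figure reproduces, and a further covariate is a refinement. This is also a repeat trial that deliberately keeps the original trial's analysis, and changing the main model gives up that identity. All of this stands. It limits the weight of the point but does not remove it, because a sensitivity analysis preserves the comparison with the original trial.

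A second reply is that the omission is not certain: the term for baseline scores is undefined, and the procedure is deferred to a cited paper. That also stands in part. The sentence nevertheless lists its covariates and speaks of the four behaviours, so baseline behaviour is the natural reading.

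Third, the benefit is unproven. The protocol reports no correlation between intention and later behaviour. The university wording is shown only for binge drinking, while the primary alcohol outcome is weekly units; Table 1 places binge sessions among the secondary outcomes. If intention explained only 1% of the residual variance, the standard error would fall by 0.5%.

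Some stronger readings are tempting but not supported:
- A reader might infer that the trial falls below 80% power without intention, by quoting 74.9% at 500 per arm. That is an unadjusted test at an assumed sample size; the planned adjustment already recovers most or all of the shortfall.
- A reader might infer narrower intervals for all four outcomes. That fails for smoking on the log-odds scale.
- A reader might argue that age is nearly constant, or that intention would repair a complete-case analysis. The protocol gives neither an age distribution nor a missing-data method.
- A reader might say that intention goes unused. It is a secondary outcome, and the research questions include change in health beliefs and mediation; it is only absent from the primary covariates.

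**Conclusion.** The point holds as a modest, near-free improvement, not as an error or contradiction. It is firm that intention is not among the named primary covariates, that it is collected at baseline for all four behaviours, and that adjusting for it would be valid.

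The size is not firm. It rests on the assumed ranges for R0² and q, and on d = 0.20 with 600 per arm analysed at six months. Under those assumptions the gain runs from about half a point to under four points of power for the three continuous outcomes. It would be worth somewhat more if six-month retention or the true effect is lower than planned. For smoking status only a gain in power can be expected, and the documents do not allow it to be quantified.

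**What to change.** In the Analyses section, replace the covariate list with: age, gender, nationality, the baseline score of the behaviour being analysed, and the baseline intention score for that same behaviour. Fix this before any outcome data are seen. The wording also settles what the baseline score means.

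Report the original trial's model, without intention, as a sensitivity analysis for all four behaviours.

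The cost is one sentence and one parameter per model. No new data are needed, because allocation follows completion of the baseline questionnaire. The small downside is that the main model would no longer be identical to the original trial's.

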## **Acknowledgements**

The study is funded by the UK National Prevention Research Initiative (NPRI) Phase 4 (grant number: MR/J0004501/1). The NPRI includes the following Funding Partners (in alphabetical order): Alzheimer's Research Trust, Alzheimer's Society, Biotechnology and Biological Sciences Research Council, British Heart Foundation, Cancer Research UK, Chief Scientist Office, Scottish Government Health Directorate, Department of Health, Diabetes UK, Economic and Social Research Council, Health and Social Care Research and Development Division of the Public Health Agency (HSC & R&D Division), Medical Research Council, The Stroke Association, Wellcome Trust, Welsh Assembly Government and World Cancer Research Fund.

Table 1. *Summary of Primary and Secondary Outcome Measures*

Measure	Baseline	One-month follow-up	Six-month follow-up
Primary Outcome Measures:			
Fruit and Vegetable Intake	x	x	x
IPAQ (Physical Activity)	x	x	x
Alcohol Use (Units)	x	x	x
Smoking Status	x	x	x
Secondary Outcome Measures:			
Number of binge sessions	x	x	x
Number of cigarettes	x	x	x
Intention (all HBs)	x	x	x
EQ-5D-3L (Health status)	x	x	x
BMI	x	x	x
Drug use	x	x	x
TPB variables/planning		x	x
AUDIT			x
Health services usage			x
Hair samples	x		x

Figure 1. *Flowchart of the Randomised Controlled Trial*
